Our primary outcome is *S. aureus* eradication at 7 days (test of cure (TOC)). Secondary outcome is eradication at 1 month (long term follow up). Study staff will administer surveys to subjects and/or their parents about risk factors hypothesized to predict treatment success. Secondary outcomes include safety, tolerability, and adherence to oral CHG. We will also examine predictors of eradication, including pathogen level factors. Pathogen-level factors will be examined using *S. aureus* whole genome sequencing, which will allow us to quantify the presence or acquisition of the *qacA/B* gene, which is associated with CHG resistance. WGS will also allow us determine if stains associated with persistence after CHG use represent pre-existing colonizing strains or acquisition of new strains.

If CHG oral rinse is efficacious at eradication, our findings will form the foundation for a larger, more comprehensive intervention to prevent recurrent SSTIs in children. If CHG oral rinse cannot decolonize the oropharynx, then investigations may need to focus on other strategies to prevent *S. aureus* disease. Regardless of results, our trial will forward the field of prevention of this extremely common and potentially deadly infection.

Structured Abstract (Do not exceed one page)

Describe the medical problem as it relates to children

- Community-associated (CA) *Staphylococcus aureus*, including methicillin-resistant *S. aureus* (MRSA), is the most commonly identified cause of skin and soft tissue infections (SSTIs) and affects children disproportionately.

State the incidence/prevalence of problem in children

- Four in 100 children in the U.S. will experience a SSTI annually, resulting in over one million infections annually, a problem further complicated in that over 50% of children who have a *S. aureus* skin infection will develop a recurrent infection.

Background that will lead to the research gap (*may use 2 sentences*)

- Our group found that, despite common belief, the most common site of colonization of *S. aureus* on the human body is not the anterior nares (nose), but the oropharynx. There are mounting data that decolonization regimens that do not eradicate oropharyngeal colonization are ineffective at preventing recurrent *S. aureus* SSTIs.

State the primary research gap this study will address

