We have several secondary hypotheses: a) decolonization of oropharyngeal *S. aureus* colonization with 0.12% CHG will be sustained at 28 days; b) recolonization of the oropharynx will come from isolates that colonize patients nose and not from development of antimicrobial resistance, including the emergence of CHG-resistant *S. aureus* strains that contain the *qac A/B* genes; and c) predictors of failure to decolonize with CHG will include poor treatment adherence, nasal *S. aureus* colonization, and younger age.

If our primary hypothesis is correct, findings will form the foundation for a larger, randomized, prospective, multi-center, placebo-controlled clinical trial comparing skin, nasal, and oropharyngeal decolonization vs. standard of care decolonization regimen for the prevention of recurrent *S. aureus* skin infections. If oral CHG rinse is unable to decolonize the oropharynx, then other more aggressive oropharyngeal *S. aureus* colonization eradication strategies in children will need to be tested.

B. Specific Aim(s) of the Project

1) Determine the efficacy of oropharyngeal decolonization among children with a history of CA-MRSA, CA-*S. aureus* or skin and soft tissue infection (SSTI). To determine if oropharyngeal *S. aureus* colonization can be eradicated, we will perform a randomized, double blind placebo-controlled controlled clinical trial comparing 0.12% oral chlorhexidine (CHG) oral rinse to placebo among children age 5-17 with *S. aureus* oropharyngeal colonization. We hypothesize that 0.12% CHG rinse will reduce oral *S. aureus* colonization better than placebo treatment. Our findings will provide “proof of principle” data on the ability of oral antiseptics to eradicate oropharyngeal *S. aureus* colonization in children.

2) Assess the safety, tolerability, and compliance of oropharyngeal decolonization among children and their caregivers. Using a structured instrument, we will survey trial participants and their parents/guardians on side effects, tolerability, and adherence of the 0.12% oral CHG rinse and placebo. Findings will serve as a counterpoint to any benefits derived from oral decolonization.

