Subjects will also be swabbed for *S. aureus* and MRSA colonization at the anterior nares and oropharynx. Testing will be performed using two methods: direct microbiology cultures and rapid molecular testing. Microbiologic cultures will be performed by culturing swabs from sites taken to identify *S. aureus* and MRSA carriage will be transported to the research microbiology laboratory at LA BioMed at Harbor-UCLA and plated within 24 hours of collection. Swabs will be processed for *S. aureus* using blood agar and CHROMagar plates for rapid identification of *S. aureus* and MRSA. All *S. aureus* and MRSA isolates will be banked for pulse-field typing, determination of SCCmec type, and presence of the PVL locus (*lukF-PV* and *lukS-PV*). Rapid molecular testing will be performed using the GeneXpert MRSA/SA platform, which is currently available at our site.

Upon confirmation of eligibility, the study coordinators will call the pharmacy to randomize the participant and obtain the oral rinse. The randomization assignment list will be generated in advance by pharmacy. Randomization procedures by an assignment list will be prepared by a computer method. To ensure adequate balance of subjects between the CHG and placebo groups, treatment allocation will be assigned using a random number generation with randomization of blocks of four subjects each. The randomization list will be kept by the pharmacy and treatment allocation randomization will not be shared with either the study staff or patients. The research pharmacists will dispense the appropriate oral rinse to the participant and their parent/guardian. Placebo will be created using the inert vehicles components of CHG, as has been done previously.⁸⁹ Participants and their parent/guardian will be given detailed instructions on the use of the oral rinse both verbally and in a handout in either English or Spanish as preferred by the participant and their parent/guardian.

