The decolonization rate will be calculated as the number of subjects who remain decolonized divided by the number of subjects, and treatment group differences as differences in these rates. The precision of estimated rates and rate differences will be expressed with two-sided confidence intervals calculated as asymptotically normal approximations to binomial or differences in binomial random variables. The level of confidence for these intervals will be 95%. Statistical significance for differences between treatment groups in cure rates will be determined from Fisher’s exact tests. The level of significance for these tests is 0.05. Factors associated with failure of decolonization in the CHG treatment group will also be examined. Based on prior investigations of *S. aureus* colonization from our group and others, these will include demographics (age, gender, race/ethnicity), co-morbidities, measures of hygiene, number of prior skin infections in the prior year, antibiotic use in the prior year, household history of skin infection, adverse effects and tolerability (see Aim 2, below), and treatment adherence. Additionally, we will examine pathogen level predictors of decolonization failure, based on molecular characterization of baseline isolates (see Aim 3). These factors will include baseline colonization with USA300 strain, presence of qac A/B gene, presence of nasal colonization, presence of nasal colonization with a strain identical to the oropharyngeal colonizing strain, and presence of nasal colonization with a strain differing from the oropharyngeal colonizing strain. Associations will be examined using Chi-squared, Fisher Exact test, Wilcoxon rank sum test, or T-test, as appropriate. Small sample size will preclude multivariable analyses of factors independently associated with failure to decolonize. This analysis will be key to identifying factors associated with decolonization failures. Identification of mutable factors associated with decolonization failure will be key towards improving the success of future efforts at oropharyngeal eradication of *S. aureus*. Identification of non-mutable factors will be key towards identifying groups that may need more intense intervention and or education.

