All subjects who have consented will have the rapid *S. aureus* test performed with results shared with the subject's parent/guardian, the subject, and the clinician, if approved by the parent/guardian. Study staff will educate and the subject's parent/guardian, and subject (if of sufficient age), the clinical significance of the results, either positive or negative. More specifically, they will be educated that currently testing for *S. aureus* oropharyngeal colonization is considered experimental and that if the test is positive, the clinical significance is unclear. They will also be educated that tens of millions, perhaps over 100 million Americans are colonized in the throat with *S. aureus*, and the vast majority do not suffer consequences of having this bacteria live in the throat. Upon request, subjects will be provided with a written copy of their results as well as a written description of the clinical significance of oropharyngeal colonization that they can share with their provider, if they wish.

Subjects with a positive screening test will undergo 3 study visits total: baseline/enrollment visit (Visit 1), Day 7 (Visit 2), and Day 28 (Visit 3). Consenting subjects will have their anterior nares and oropharynx swabbed at Visits 1, 2, and 3. A survey will be administered at the initial visit and a follow-up survey will be administered at Visits 2, and 3. The survey administered at Visit 1 will collect information about demographics, medical history, and behavioral risk factors for skin and soft tissue infection and colonization. Subjects will be randomized to 0.12% CHG oral rinse or placebo use for 7 days. All subjects will receive educational materials regarding *S. aureus* and skin infections and their prevention. Those randomized to the intervention will receive additional verbal and written information on use of CHG oral rinse. The survey administered at Visit 2 will collect information about the adherence, tolerability, and adverse events during the intervention period. The survey administered at Visit 3 will collect information about (late) adverse events, changes in household dynamics and individual behavior (e.g., hygiene) that may affect results of Visit 3 nasal and oropharyngeal colonization studies.

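### Adherence is a secondary outcome and a hypothesised predictor of failure, but it rests on a survey alone; measuring returned rinse at the existing Day 7 visit would be a cheap improvement

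*Combined protocol and SAP*

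**What the plan says.** The Scientific Abstract gives adherence outcome status: "Secondary outcomes include safety, tolerability, and adherence to oral CHG". In Hypothesis(es) and Aims, secondary hypothesis (c) states that "predictors of failure to decolonize with CHG will include poor treatment adherence", followed by nasal colonization and younger age. The list of factors for the CHG-arm failure analysis, under Data Analyses and Data and Safety Monitoring, ends with "adverse effects and tolerability (see Aim 2, below), and treatment adherence".

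The measurement is described in three places, each time as a survey. Specific Aim 2 reads: "Using a structured instrument, we will survey trial participants and their parents/guardians on side effects, tolerability, and adherence" of the two rinses. The Aim 2 methods repeat that a survey will cover side effects, tolerability and compliance. The Human Subjects section gives the timing: "The survey administered at Visit 2 will collect information about the adherence, tolerability, and adverse events during the intervention period". The Follow-up visits section also lists what the Visit 2 survey covers, but does not mention adherence there.

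On supply, the Baseline visit section says: "The research pharmacists will dispense the appropriate oral rinse to the participant and their parent/guardian". It does not say that the amount dispensed is recorded or that the container comes back. No dosing diary, electronic record or drug assay appears anywhere, and no definition of an adherent participant is given. A Day 7 clinic visit is scheduled for every randomised child.

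On interpretation, the Scientific Abstract says: "If CHG oral rinse cannot decolonize the oropharynx, then investigations may need to focus on other strategies to prevent" *S. aureus* disease.

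**The concern.** Treatment is two uses a day for 7 days, 14 in all, taken at home by children aged 5 to 17, with no supervision of home use described. The protocol lists altered taste among the known effects of the rinse, so skipped uses are plausible. If families report more use than took place, three things suffer:

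- The Aim 2 compliance estimate is too high.
- Children who did not use the rinse are counted among the adherent, which weakens the association between adherence and failure. The protocol calls finding changeable causes of failure key to later work, and adherence is an obvious one.
- A low eradication rate in the CHG arm is harder to interpret. It may reflect a rinse that does not work or one that was not used, and the suggested response, looking to other strategies, fits the first explanation better than the second.

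**Working it through.** **Inputs from the documents (Power and Sample Size; Follow-up visits).** Expected eradication is 50% with CHG and 10% with placebo, alpha is 0.05, there are 27 completers per arm, and attrition is 10%.

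**Assumptions not in the documents.** A share q of the CHG arm hardly uses the rinse and clears at the placebo rate of 10%; the rest clear at 50%. The survey detects a share d of the non-users, and users are always reported as users. I take q = 20-40% and d = 25-75%. Tests are two-sided.

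**1. The plan's own figure.** The usual two-proportion formula without correction gives [1.96 × √(2 × 0.3 × 0.7) + 1.036 × √(0.25 + 0.09)]² / 0.4² = 21.96, or 22 per arm. The continuity correction gives (21.96/4) × [1 + √(1 + 4/(21.96 × 0.4))]² = 26.7, so 27 per arm and 54 in total, as stated. With 10% attrition, 54/0.9 = 60, as stated. How adherence is measured does not enter this calculation.

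**2. Why the primary result cannot answer the question by itself.** The CHG-arm rate is 10% + 40% × (1 − q). If half the children use a fully effective rinse, it is 10% + 40% × 0.5 = 30%. If all use a rinse with half the expected effect, it is 10% + 20% = 30%. Only the adherence data can separate the two.

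**3. Effect of over-reporting.**

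- Reported adherence = 1 − q × d.
- Eradication among reported adherers = [(1 − q) × 0.50 + q × (1 − d) × 0.10] / (1 − q × d).

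| True non-use q | Detected d | True adherence | Reported adherence | Eradication among reported adherers |
|---|---|---|---|---|
| 20% | 75% | 80% | 85% | 47.6% |
| 20% | 25% | 80% | 95% | 43.7% |
| 30% | 50% | 70% | 85% | 42.9% |
| 40% | 75% | 60% | 70% | 44.3% |
| 40% | 25% | 60% | 90% | 36.7% |

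With perfect measurement the last column would be 50% throughout.

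**4. The adherence-failure test.** Take 27 CHG children and q = 30%: 27 × 0.30 = 8.1, so 8 non-users and 19 users. Fisher's exact test, with every possible table enumerated:

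- Perfect measurement, 19 at 50% against 8 at 10%: power 42%.
- Half of the non-users missed, so 23 reported users against 4 reported non-users. The reported users clear on average at (19 × 0.50 + 4 × 0.10)/23 = 43%. Power is about 4%.

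The second figure is so low because the non-user group shrinks to 4. Even if none of those 4 clears, at least 14 of the 23 must clear for p ≤ 0.05, while about 23 × 0.43 = 9.9 are expected to.

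**The case against.** Several stronger readings are tempting, and the documents do not support them.

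- **A reader might infer that this costs the trial its power.** At 27 per arm, Fisher power for the primary test is 87% with full use and 44% with 40% non-use. That loss comes from non-use, not from how non-use is measured, and weighing containers afterwards restores none of it. The primary comparison is not biased and the sample size stands.
- **A reader might infer that an ineffective rinse cannot be told from an unused one at all.** That goes too far. Children and parents are asked directly, with a structured instrument, at the end of a seven-day course, and admitted non-use is informative. What is missing is any check on that report. That the answers are recalled is itself an inference, from a Day 7 survey with no diary.
- **A reader might infer a firm stopping rule for CHG.** The abstract says only that other strategies may be needed, and the hypotheses section speaks of testing more aggressive oropharyngeal ones. The plan also names poor adherence as a possible cause of failure and intends to examine it.
- **A reader might assume that all families return with a container of known content.** The plan allows for 10% attrition and states neither a dispensed amount nor an amount per use.

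Other points against stand in part. With about 23 reported adherers, the 95% half-width is 1.96 × √(0.43 × 0.57/23), about 20 percentage points, so a shift from 50% to 43% lies within sampling error. The predictor test is weak even with perfect data, and the plan concedes that small numbers rule out multivariable work. The gargling criterion, the demonstration, the written instructions and the timing device support correct use, though they measure nothing. Missing volume may have been spilled or discarded and does not show a full gargle.

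These points limit the gain. They do not remove the case for an inexpensive check on an outcome that the plan itself has chosen.

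**Conclusion.** The point holds as a cheap improvement, not as an error that threatens the trial. Adherence has four roles in the plan and a single unverified source. Under the stated assumptions, reported adherence would be 70-95% against a true 60-80%, and eradication among reported adherers would read 37-48% instead of 50%. With 30% non-use and half of it missed, power for the adherence-failure test would be about 4% instead of about 42%. Non-use, survey detection and clearance at the placebo rate among non-users are all assumptions, so these figures show direction and possible size and are not forecasts. What is affected is the Aim 2 adherence estimate, the predictor analysis and the reading of a weak or null CHG result.

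**What to change.** In the Baseline visit, Follow-up visits and Human Subjects sections:

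- Have the pharmacy record the weight or volume dispensed to each participant.
- Tell families in both arms, in the same words, to bring the container to Visit 2.
- Have staff who do not know the allocation record what remains.
- Compute percent of expected use from the per-use amount in the study's own rinse instructions. The protocol should state where that amount is given.
- Use this measure together with the survey as the adherence variable in Aim 2 and in the CHG-arm failure analysis, and state in advance how the two are combined. Treat participants with an unreturned container as survey-only, and report how many there are.
- Keep the survey for technique and reasons for missed uses, and add adherence to the Visit 2 survey content in the Follow-up visits section so that it agrees with the Human Subjects section.

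The cost is a pharmacy entry, a line in the handout, one measurement at an existing visit and a short analysis rule. No visit is added and the sample size does not change. Some containers will not come back, about 10% attrition is expected, and volume removed does not show gargling, so the ambiguity is reduced and not removed. The rule has to be in place before enrolment, because the information is lost once containers are thrown away.
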